## **5.2 Participation Criteria**

Eligibility and applicable participant medical history will be overseen by a medical doctor throughout the course of the study to assess participant safety. About 85% of research requests can be completed by the protocol procedures, herein. Some research requests cannot be fulfilled using the procedures discussed below. These requests will be submitted to the IRB as an amendment to this protocol. A medical doctor will review these exceptional collection requests to assess participant safety.

### **5.2.1 Health Condition Group**

#### **Health Condition Group Inclusion Criteria:**

- Persons 18 to 85 years of age at the date of informed consent.
- If presenting with a history of a specific condition, the diagnosis is confirmable in the medical record.
- Understands the procedures and requirements of the study by providing written informed consent (or verbal assent if a legally authorized representative will sign the ICF), including consent for authorization for protected health information disclosure.

#### **Health Condition Group Exclusion Criteria:**

- Persons younger than 18 years of age or older than 85 years of age at the date of informed consent.
- Receipt of blood products 30 days before the study blood draw.
- Receipt of an investigational (unapproved) drug 30 days before the study blood draw.
- A confirmable disease of any medical condition that would increase potential phlebotomy risks. Such medical conditions include:
  - Severe or untreated cardiovascular diseases;
  - Bleeding disorders;
  - Late-stage chronic kidney disease; and/or
  - Conditions associated with chronic anemia.
- Pregnancy
- Has donated a unit of blood within the last 2 months at the date of informed consent.

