Drawing up to 100mL for the health condition group will allow the biobank to collect enough blood from isolating several sub-products from the whole blood, such as serum, plasma, peripheral blood mononuclear cells (PBMCs), and genetic material (DNA/RNA), which are commonly used in biomedical research. A blood draw will provide biological tissue to research and expose participants to minimal risk. A blood draw allows participants flexibility in scheduling the draw, either at a site or in the comfort of their home.

Due to a potential increase of phlebotomy risks for people with certain medical conditions such as cardiovascular diseases, bleeding disorders and late-stage kidney problems, the exceptive condition group will have only up to 60mL drawn to minimize these risks.

The study aims to collect biological tissue from multiple populations to support and advance biomedical research. Drawing a large volume of blood from healthy donors will provide more control biosamples for researchers (posing minimal risk to the participant). Allowing the study efforts to concentrate on collecting samples from various populations to service more research fields.

The control group may have up to 180mL of blood drawn for the study if determined that the participants health will not compromise their safety during the draw. The amount of 180mL is about one-third of the blood drawn during a blood donation and is considered by the Department of Health and Human Safety (HHS) to pose minimal risk to the participant. The study would like to have the potential to draw up to 180mL if the health of the participant allows this amount biological tissue to be collected from one appointment. Since the major risk and discomfort from venipuncture comes from being stuck with the needle, the study believes that a one-time blood draw of a larger volume would be potentially more comfortable for a healthy individual versus undergoing multiple venipunctures.

Participant health will be assessed prior to phlebotomy to determine maximum blood draw volume for all cohorts.

For all research requests that are not covered within this protocol, independent protocol amendments addressing the procedural changes may be drafted to address and minimize possible study risks. A medical practitioner will review the procedural amendments for safety assessment and submit to the IRB for review.

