##### **Control Group Exclusion Criteria:**

- Persons younger than 18 years of age or older than 85 years of age at the date of informed consent.
- Receipt of blood products 30 days before the study blood draw.
- Receipt of an investigational (unapproved) drug 30 days before the study blood draw.
- A confirmable diagnosis of any medical condition that would increase potential phlebotomy risks. Such medical conditions include:
  - Severe or untreated cardiovascular diseases

- Bleeding disorders;
- Late-stage chronic kidney disease; and/or
- Conditions associated with chronic anemia.
- Pregnancy
- Requires a Legally Authorized Representative (LAR) for the study informed consent.
- Has donated a unit of blood within the months at the date of informed consent.

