##### **5.3.5.1 Blood Collection**

A blood draw is the most common type of biospecimen collection procedure, making up about

95% of biospecimen requests. Blood will generally be collected by venipuncture from a medical professional certified in phlebotomy. Participants may also be asked to provide a microsample of blood via fingerstick. Fingerstick samples will be collected on a blood card, such as a dried blood spot (DBS) card, or into a microtainer. Researchers may use the blood cards for specific testing of biomarkers or isolating genetic material.

Blood collection volumes are dependent on which cohort the participant is placed and self-reported medical data (see Table 1). Blood may be collected every 7 days, but the total volume collected during a 6-week period may not exceed the Table 1 volumes. Maximum blood collection volumes in Table 1 may be collected at one time

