**Standard Questions:**

Investigational Drug in past 30 days?	Weight (in lbs)
Currently Pregnant?	Height (Feet)
Recent Blood Donation?	Inches
	Calculated BMI
	Total Blood Volume

---

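### The 2-month blood-donation exclusion looks back only from the consent date, so a unit donated after consent bars no later study draw under any stated rule

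*Protocol*

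**What the plan says.** The donation criterion for the health condition group (section 5.2.1) reads "Has donated a unit of blood within the last 2 months at the date of informed consent". The same wording stands in the exceptional condition list of section 5.2.2 and in all three Synopsis lists. The control list in section 5.2.3 keeps the consent anchor but has lost the interval: "Has donated a unit of blood within the months at the date of informed consent". The Synopsis control list gives it as 2 months.

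Two other look-back criteria in the same lists are anchored to the draw. One is "Receipt of blood products 30 days before the study blood draw"; the investigational-drug criterion follows the same pattern.

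Section 5.3.5.1 sets the repeat-draw rule: "Blood may be collected every 7 days, but the total volume collected during a 6-week period may not exceed the Table 1 volumes". Table 1 sets the limits at 100 mL (health condition), 60 mL (exceptional condition) and 180 mL (control), and the whole limit may be taken at one time.

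Several general safeguards apply:
- Section 4.1: "Participant health will be assessed prior to phlebotomy to determine maximum blood draw volume for all cohorts".
- Section 5.2: "Eligibility and applicable participant medical history will be overseen by a medical doctor throughout the course of the study".
- Section 5.3, item 5a: medical history is taken into account at the blood draw.
- Section 5.3.5.1, below Table 1: the phlebotomist asks how the participant feels and decides whether to go ahead.
- Section 5.3.6: health history is collected before the draw.
- Appendix C: the example health profile has a field headed "Recent Blood Donation".

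**The concern.** The protocol treats a unit given in the previous 2 months as reason enough to keep someone out, even in the exceptional condition group, where the study takes no more than 60 mL. The reason for such a rule is blood recently lost, and it applies equally at a second or third study draw. Because the criterion is judged once, at consent, a donation made afterwards is invisible to it.

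What is at stake is participant safety. The exposure matters most in the exceptional condition group, whose volume is restricted because the protocol regards its phlebotomy risk as raised.

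**Working it through.** The protocol states no figure for combined blood loss, so there is none to reproduce. The check sets the anchors side by side and then sizes the possible exposure.

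**Anchors**

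| Rule | Measured from | Catches a donation made after consent? |
|---|---|---|
| Donation, 2 months (six lists) | Date of consent | No |
| Blood products, 30 days | Study blood draw | Not about donation |
| Investigational drug, 30 days | Study blood draw | Not about donation |
| Table 1 limit, 6 weeks | Study collection volume | No; outside donations are not mentioned |
| Pre-draw assessment, medical oversight, history, profile field | No interval given | Possibly, at staff discretion |

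The donation anchor and the draw coincide only when both fall on the same day. Section 4.2 places consent before the collection or collections and does not require it again at each draw. Section 5.3.4 allows electronic signature from home or through a website, so even a first draw may come later than consent.

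**Size of a unit.** Section 4.1 says: "The amount of 180mL is about one-third of the blood drawn during a blood donation". This gives 3 × 180 = 540 mL, approximately. As a sensitivity range I assume 450 to 500 mL; that range is not in the protocol.

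**Donation plus one maximum study draw** (unit + Table 1 limit)

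| Cohort | Limit (mL) | Unit 540 mL | Unit 450 to 500 mL (assumed) |
|---|---|---|---|
| Control | 180 | 540 + 180 = 720 | 630 to 680 |
| Health condition | 100 | 540 + 100 = 640 | 550 to 600 |
| Exceptional condition | 60 | 540 + 60 = 600 | 510 to 560 |

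**Visits inside the window.** Two months is 59 to 62 days. With 7-day spacing, draws could fall on days 1, 8, 15, 22, 29, 36, 43, 50 and 57 after a donation, which is 9 visits. The number of visits does not raise the permitted volume. That is limited to one Table 1 amount in any 6 weeks, and the limit can renew once within 2 months (for example, day 1 and day 43). The most the study could take in the window is therefore 2 × 180 = 360, 2 × 100 = 200 or 2 × 60 = 120 mL.

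**With the window anchored to each draw,** the study volume permitted in the 2 months after a donation would be 0 mL in every cohort.

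**The case against.** The strongest reply is that the scenario is narrow. The Synopsis calls the study cross-sectional and puts active participation at one to two hours, and section 4.1 favours a single larger draw over repeated venipuncture. For anyone who consents and gives one sample at the same visit there is no gap. The gap needs a later draw, an outside donation in between, and pre-draw checks that miss or disregard it. The protocol gives no frequency for any of these. This stands, and it limits the size of the point.

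A second reply is that safeguards exist, above all the phlebotomist's decision on the day. This also stands, in part: what is missing is a fixed interval, not any means of stopping a draw. But the question described is whether the participant feels healthy, and the three questions for a 180 mL draw cover weight, age and difficult veins. Neither names donation. Medical oversight of eligibility does not help by itself, because the criterion overseen looks back only from consent.

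Third, the comparison criteria refer to the study draw in the singular, so they do not clearly govern repeat draws either. Operating procedures not shown might say when the donation question is asked. Both are fair. They weaken the contrast between anchors, but they do not put a donation rule for later draws into the protocol.

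Finally, most of each combined total is the participant's own donation, and no combined limit is stated. That is true. The totals describe what the text permits; they do not demonstrate harm.

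**Conclusion.** The concern holds. Followed exactly, the protocol lets a participant who donates a unit after consent be drawn again, up to the full Table 1 volume, with no criterion breached. Donation plus one maximum draw could reach about 720, 640 or 600 mL (control, health condition, exceptional condition) on the protocol's implied unit, or 630 to 680, 550 to 600 or 510 to 560 mL if a unit is 450 to 500 mL.

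The point is confined to draws after the consent date. It rests on repeat or delayed draws actually occurring, at a frequency the protocol does not give, and on the discretionary checks not leading to deferral. It should be corrected, because the protocol's own reasoning at entry applies unchanged at later draws. Confidence is medium, given the unknown frequency and the operating procedures not seen. The missing interval in section 5.2.3 is a separate, minor wording fault whose intended value is clear from the Synopsis.

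**What to change.** In all six exclusion lists, replace the donation criterion with: *Has donated a unit of blood within the 2 months before any study blood draw.* Applied to section 5.2.3, this also restores the missing interval.

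In section 5.3.5.1, require staff to ask the existing donation question from the health profile at each draw visit, and to defer the draw if a unit was given within the preceding 2 months.

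The cost is an edit to six lists and one procedural paragraph, one existing question repeated at each draw visit, and an occasional deferred draw.

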### **5.2.2 Exceptive Condition Group**

#### **Exceptive Condition Group Inclusion Criteria:**

- Persons 18 to 85 years of age at the date of informed consent

- If presenting with a history of a specific condition, the diagnosis is confirmable in the medical record.
- A confirmable diagnosis of any medical condition that would increase potential phlebotomy risks. Such medical conditions include:
  - Severe or untreated cardiovascular diseases (including a stroke or myocardial infarction within the last 2 months)
  - Bleeding disorders;
  - Late-stage chronic kidney disease;
  - Splenomegaly;
  - Pregnancy; and/or
  - Conditions associated with chronic anemia.
- Understands the procedures and requirements of the study by providing written informed consent (or verbal assent if a legally authorized representative will sign the ICF), including consent for authorization for protected health information disclosure.

#### **Exceptional Condition Group Exclusion Criteria:**

- Persons younger than 18 years of age or older than 85 years of age at the date of informed consent.
- Receipt of blood products 30 days before the study blood draw.
- Receipt of an investigational (unapproved) drug 30 days before the study blood draw.
- Has donated a unit of blood within the last 2 months at the date of informed consent.

#### **5.2.3 Control Group**

##### **Control Group Inclusion Criteria:**

- Persons 18 to 85 years of age at the date of informed consent.
- Understands the procedures and requirements of the study by providing written informed consent (or verbal assent if a legally authorized representative will sign the ICF), including consent for authorization for protected health information disclosure.

##### **Control Group Exclusion Criteria:**

- Persons younger than 18 years of age or older than 85 years of age at the date of informed consent.
- Receipt of blood products 30 days before the study blood draw.
- Receipt of an investigational (unapproved) drug 30 days before the study blood draw.
- A confirmable diagnosis of any medical condition that would increase potential phlebotomy risks. Such medical conditions include:
  - Severe or untreated cardiovascular diseases

- Bleeding disorders;
- Late-stage chronic kidney disease; and/or
- Conditions associated with chronic anemia.
- Pregnancy
- Requires a Legally Authorized Representative (LAR) for the study informed consent.
- Has donated a unit of blood within the months at the date of informed consent.

### **5.3 Participant Procedures**

The components of this study include:

1. Participant recruitment
2. Pre-consent Inclusion/Exclusion Screening
  - a. Collection of demographic data
  - b. Collection of self-report health history
3. Cohort Placement
  - a. Health Condition Group
  - b. Exceptional Condition Group
  - c. Control Group
4. Study enrollment and Informed Consent process
5. Biospecimen Collection
  - a. Blood draw by a certified medical professional. Medical history considered.
  - b. Minimal risk biospecimen collection
  - c. Biospecimens that require a clinical procedure and are considered more than minimal risk
    - i. Participant signs procedure-specific ICF
    - ii. Procedures performed by trained medical professionals such as physicians and nurses and at study-approved sites
6. Participant surveys, questionnaires, and PROs
7. Recovery time assessment by the study staff depending on the type of specimen collected, medical history, and health of the individual.
8. Data is securely stored through electronic and physical means.

Please see Appendix C for participant safety workflow.

#### **5.3.1.1 Online Recruitment**

Participants may be recruited online through patient advocacy websites, social websites such as Craigslist, Sanguine Bioscience's Facebook page, and Sanguine's website. The Sanguine website provides information to potential participants about the Sanguine biobank through its website, explaining study objectives and participation requirements. Participants may also receive updates regarding condition-specific current active biospecimen collections.

Participants can also refer friends and family to participate in the biobank study. Current participants can enroll on Sanguine's website. The referral recruitment method is initiated and controlled solely by study participants.

All potential participants recruited/referred to Sanguine's biobank study must consent to be contacted, permitting study staff to contact them. Through the successful completion of study procedures and referral, participants may be awarded points.

#### **5.3.2 Potential Participant Inclusion/Exclusion Screening**

From the screening process, study staff will determine if the potential participant can enroll in the study or not. After the potential participant has signed up, a study staff member will contact the potential participant to introduce the study and evaluate participant inclusion/exclusion. During this process, direct participant identifiers will be collected. Data collected include but are not limited to a physical address, date of birth, and general medical history associated with a specific condition. Please see Appendix D for an example of medical information collected.

#### **5.3.3 Potential Participant Cohort Placement**

After the screening process, trained study staff will review the self-reported medical history to determine cohort placement. If the participant does not report any medical conditions or remarkable medical history, they will be placed in the control cohort. If the participant has reported a medical condition that could potentially increase the presentation of risks associated with phlebotomy, such as bleeding disorders, severe or untreated cardiovascular diseases, late-stage chronic kidney diseases, pregnancy, or splenomegaly, the participant will be placed in the exception condition cohort. This cohort identification is designed to distinguish participants who require additional protection during a phlebotomy procedure. All other participants will be placed

in the health condition group. If a participant does not meet inclusion/exclusion criteria, they will be notified that they cannot participate in this study.

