### **3 STUDY OBJECTIVES & PURPOSE**

The primary study objective is to collect, preserve, and/or distribute annotated biospecimens and associated medical data to institutionally approved, investigator-directed biomedical research to discover and develop new treatments, diagnostics, and preventative methods for specific and complex conditions.

To further study genotypic and phenotypic characteristics of specific and complex health conditions, the Sponsor may establish its biorepository to facilitate viable experimental results by supplying the research community with consistent, high-quality specimens. Sanguine BioSciences, Inc. (hereinafter, Sanguine) may collect biospecimens from health conditions participants and controls participants. Peripheral blood mononuclear cells (PBMC), serum, DNA/RNA, protein, and other blood portions may be extracted from blood samples and stored for future research. Other biospecimens that may be donated and stored include but are not limited to saliva, sputum, urine, hair, skin, nail clippings, stool, and semen. Demographically matched control samples may be collected to give researchers a baseline to compare against health condition samples. Control donors are considered participants who have not been clinically diagnosed with a medical condition.

Eventually, Sanguine may develop participant-derived induced pluripotent stem cells (iPS cells) to develop disease-specific cell lines that can be expanded in culture for research and development purposes only. The cells that we would obtain from participants blood do not divide in culture, and therefore will be available to a limited number of researchers. However, one can genetically transform those cells to divide. These cells are very similar to embryonic stem cells (cells that divide and transform into all types of cells – like nerve cells, skin cells, etc.)—allowing more of the participants cells to researchers working in specific conditions. The advantage of iPS cells – which are very similar to embryonic stem cells – is that they are not derived from human embryos, eliminating the ethical concern. By providing these samples to researchers, Sanguine will facilitate the pre-clinical analysis and correlation of genotypes with phenotypes (such as clinical outcomes).

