### **5.3.10 Collection of Protected Health Information (PHI)**

Participants will have their protected health information collected in two ways: self-reported data and a thorough review of their medical records. Upon enrollment, participants will be asked to authorize the release of their health information. Participants who deny this authorization may affect their enrollment within the biobank study. Upon receiving this authorization, study staff will request medical data from the appointed healthcare provider. This data will be secured by physical, electronic, and administrative means.

The biobank has security measures to protect the participant's PHI and are discussed in Section 6 and Section 7.

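### Cohorts are assigned from self-report while eligibility turns on a confirmable diagnosis, and no step checks the cohort against the medical record obtained later

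*Protocol*

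**What the plan says.** **Placement.** Section 5.3.3 states that "trained study staff will review the self-reported medical history to determine cohort placement". Its rule for controls is: "If the participant does not report any medical conditions or remarkable medical history, they will be placed in the control cohort". The route to the exceptional cohort begins "If the participant has reported a medical condition that could potentially increase the presentation of risks associated with phlebotomy". Everyone else goes to the health condition group.

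**Eligibility.** Section 5.2.1 excludes from the health condition group "A confirmable disease of any medical condition that would increase potential phlebotomy risks". Section 5.2.2 admits to the exceptional group "A confirmable diagnosis of any medical condition that would increase potential phlebotomy risks", and section 5.2.3 uses the same words to exclude from the control group. Section 5.2.1 also requires a presenting history to be confirmable in the medical record. The synopsis version of that criterion accepts other verification, self-report included.

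**Definition of a control.** Section 3: "Control donors are considered participants who have not been clinically diagnosed with a medical condition".

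**Records.** Section 5.3.10 asks for authorization at enrollment, and then: "Upon receiving this authorization, study staff will request medical data from the appointed healthcare provider". On refusal it says only: "Participants who deny this authorization may affect their enrollment within the biobank study".

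**Volume.** Table 1 sets maxima for a 6-week period of 100 mL (health condition), 60 mL (exceptional) and 180 mL (control). Section 5.3.5.1 ties the volume to the cohort and to self-reported data, and allows collection every 7 days within those totals.

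**The concern.** One decision is governed by two kinds of evidence. Placement asks what the participant reports. The criteria and the definition of a control ask what has been, or can be, documented. The cohort sets the maximum blood volume and also supplies the case or control label. If the two kinds of evidence disagree, a person can stand in a cohort whose own criteria exclude them. The protocol then collects the document that would show this, but does not say that anyone compares it with the placement.

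Two things are at stake: which volume limit governs later draws, and whether a client comparing cases with controls can rely on the cohort label. Section 2.3 presents the comparison of a condition-specific population with a control population as central to the repository's purpose.

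**Working it through.** The protocol gives no figure on this point to reproduce, so the check is mainly a comparison of the text.

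**1. Order of steps.** Section 5.3 lists screening on self-reported history as step 2, cohort placement as step 3, consent and enrollment as step 4, and collection as step 5. Section 5.3.10 puts the request for records after authorization at enrollment. The synopsis gives about one hour, and up to two, for enrollment and collection together. That no record has been seen before the first draw is therefore an inference from sequence and timing, not a statement in the text. What can be said is that no step requires a record to be seen.

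**2. Reported against documented, for a risk condition named in both 5.2.2 and 5.2.3 (for instance late-stage kidney disease).**

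| Condition reported? | Confirmable in the record? | Placement under 5.3.3 | Criteria in 5.2 | Agree? |
|---|---|---|---|---|
| Yes | Yes | Exceptional | 5.2.2 admits; 5.2.1 and 5.2.3 exclude | Yes |
| Yes | No | Exceptional | 5.2.2 not met; 5.2.1 inclusion not met either | One outcome under 5.2: not enrolled |
| No (and nothing else reported) | Yes | Control | 5.2.3 excludes; 5.2.2 would admit | **No** |
| No (and nothing else reported) | No | Control | 5.2.3 does not exclude | Yes |

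The third row is the conflict. The limit applied is up to 180 mL, while the cohort whose risk-condition criterion the person meets has 60 mL: 180 / 60 = 3, and 180 − 60 = 120 mL apart.

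**3. Label.** Not reporting a condition (5.3.3) is a looser test than not having been diagnosed (section 3). Any documented but unreported condition, whether or not it raises phlebotomy risk, passes the first and fails the second.

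**4. After the record arrives.** No passage has the cohort revisited. With draws allowed every 7 days, and a limit that applies to each 6-week period, the control limit stays in force for later draws even when the record on file contradicts it.

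**5. Illustration of what a wrong label could cost a client.** None of these inputs is in the documents. Assume two equal groups, a standardised difference d = 0.3, two-sided 5%, 90% planned power, and a share m of controls who in truth have the disease under study and resemble the cases, with the standard deviation unchanged.

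- Planned size: n = 2(1.96 + 1.2816)² / 0.3² = 233.5, so 234 per group.
- Observed difference: 0.3(1 − m).
- Power: Φ(0.3(1 − m)√(234/2) − 1.96).
- Size needed to restore 90%: 233.5 / (1 − m)², rounded up.

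| m (assumed) | Power | n per group needed |
|---|---|---|
| 2% | 88.9% | 244 |
| 5% | 86.9% | 259 |
| 10% | 83.2% | 289 |
| 20% | 73.8% | 365 |

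**The case against.** **Confirmable does not mean confirmed.** Screening on self-report for a diagnosis that can later be documented is a sequence, not a contradiction. This stands for a condition that is both reported and documented. It does not help when the condition is documented but not reported.

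**Safeguards exist.** A medical doctor oversees eligibility and history (5.2), health is assessed before phlebotomy to set the maximum volume in every cohort (4.1), the phlebotomist assesses the participant (5.3.5.1), control draws at the full volume need further questions (5.3.6), and Table 1 gives maxima rather than assigned volumes. These reduce the volume risk. None of them names a record check, and the history review in 5.3.6 is again of self-report. An investigator recruiting in clinic may already hold records, but no step requires looking at them.

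**Clients receive more than a label.** Section 5.7 delivers the associated health information with the order, so a client may be able to see the discrepancy. This limits the harm: the problem is a label that may contradict the data beside it, not a label with nothing beside it.

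**A re-check may sit in a procedure not shown.** That is possible, but the conflict between 5.2.3 and 5.3.3 is in the protocol itself.

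**Two stronger readings are tempting and not supported.** First, a reader might infer that someone who reports a risk condition that no record confirms could still enter the 100 mL cohort, because the exclusion in 5.2.1 covers only confirmable disease. But the inclusion rule in 5.2.1 also requires a presenting history to be confirmable, and 5.3.3 sends only the remaining participants to that group, so under section 5.2 the person is not enrolled. If the synopsis standard is used and carries over to the exclusion, the report itself triggers it. Second, a reader might infer that every case-control comparison is diluted. Dilution of the kind shown needs mislabelled controls who have the disease the client is studying; an unrelated unreported condition does not produce it.

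**Conclusion.** The point holds in a limited form. Section 5.3.3 decides on what is reported, while sections 5.2.1 to 5.2.3 and section 3 decide on what is confirmable or diagnosed. The synopsis and 5.2.1 also disagree on whether self-report can verify a condition in the health condition group. The conflict bites for a participant with a documented but unreported condition. If it is a listed risk condition, that person is placed under a limit of up to 180 mL although 5.2.3 excludes them and 5.2.2 would admit them under 60 mL. The protocol obtains the record and never sets it against the placement.

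How many participants this touches cannot be derived from the documents. The power figures are an illustration under assumed misclassification with the disease under study, not an estimate for this repository. The textual conflict does not depend on them. No view is taken here on which volume limit or evidence rule is right.

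**What to change.** 1. Reconcile the synopsis criteria, sections 5.2.1 to 5.2.3 and section 5.3.3 to one evidence standard, so that each participant's history leads to one outcome. Which standard to adopt is the sponsor's medical decision.
2. Add to section 5.3.10 that, when the record arrives, it is compared with the cohort, and that the cohort and label are corrected under the reconciled criteria if they disagree, including for any later draw.
3. Add to section 5.7 a field released with each specimen stating whether the cohort label is record-confirmed or rests on self-report only. The second value also covers participants who refuse authorization but are still enrolled. For samples shipped directly to the researcher, the field may follow the specimen.

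The cost is protocol wording, one extra check on records already being collected, and one data field. No added participant visit or specimen is needed.
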